3.9 Data Collection

In this study, the principal investigator and research assistant will obtain data using a standardly developed data-collection tool.

3.10 Data Analysis

3.10.1 Interim analysis

This study will conduct two interim analysis and will be done at the midpoint of data collection and at 90% data collection by the DSMB which will be independent from the day to day staff working on the study which will meet at the midpoint of the study for Interim analysis and study progress review.

3.10.2 Data Safety Monitoring Board (DSMB)

A data safety monitoring board will be identified and they will ensure quality, subject safety and provide independent advice to the study team regarding progress and appropriateness of study continuation. It will be composed of 3 members: 1 Orthopaedic Surgeon 1 Pharmacologist, 1 Clinical Epidemiologist, and 1 Ethicist and will meet when 50% data collection completed and 90% completed to perform an interim analysis.

A Bonferroni approximation will be applied during the planned interim analysis for efficacy. For the interim analysis, the critical value for the 2-degree-of-freedom omnibus test will be set to have $\alpha = 0.0001$

3.10.3 Stoppage rules / discontinuation

These shall include the following

- Serious Adverse Events and toxicity data compromising participant safety.
- When noted a large efficacy effect.

The DSMB may recommend stopping the study based on their reviews. Because the DSMB could stop the trial for safety concerns as well as for a large efficacy benefit, there could be multiple opportunities to reject the null hypothesis.

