NDA	- NATIONAL DRUG AUTHORITY
SOMREC	- SCHOOL OF MEDICINE RESEARCH AND ETHICS COMMITTEE
TXA	- TRANEXEMIC ACID
UBTS	- UGANDA BLOOD TRANSFUSION SERVICES

ABSTRACT

Background: Major Perioperative blood loss is one of the complications of open femoral shaft fracture intramedullary nailing surgery with average blood loss estimated at 1500mls. There is need for strategies to reduce on this blood loss. Antifibrinolytics such as tranexemic acid have been successfully used to reduce perioperative blood loss in other orthopaedic procedures.

However effectiveness of tranexemic acid use during open femoral shaft fracture intramedullary nailing surgery has not been studied in our setting.

Aim: To assess the effectiveness of intravenous tranexemic acid in reduction of perioperative blood loss, transfusion rates in patients undergoing open femoral shaft fracture intramedullary nailing surgery.

Methods: This will be an open label single arm study. Patients scheduled for open femoral shaft fracture intramedullary nail fixation surgery will receive preoperative tranexemic acid at 15mg/kg. Blood loss using difference between pre and post-operative hemoglobin, blood transfusion rates and adverse events in the peri operative period will be measured.

Utility: The results of this study will reveal effectiveness of tranexemic acid in reducing perioperative blood loss during open femoral shaft fracture surgery in this setting. This information will be useful in designing protocols for prevention of perioperative blood loss for femoral shaft fracture surgery.

OPERATIONAL DEFINITIONS

Peri-operative

- Period from start of surgery to 72 hours after the Surgery

ORIF

- Open intramedullary nailing of femoral shaft fractures.

CHAPTER ONE

INTRODUCTION

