3.1 Study design

This will be an open label single arm trial involving adult patients undergoing open intramedullary femoral shaft nail fixation at Mulago National Referral Hospital.

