3.4 Study Duration

The study will be conducted over a period of 3 months from the date of ethical approval.

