3.7.7 Post-operative care

Patients in the immediate post-operative period will be monitored by the nurses on their primary wards noting vitals (Blood Pressure, Pulse Rate, Respiratory Rates and observe blood soiling of the surgical site dressing). Adequate analgesia will be given to the patients and mobilization in or out of bed will be instituted 12 hours following surgery with guidance of the physiotherapist as per patient tolerability.

Principal investigator together with the surgeons and residents on the primary wards will clinically review the patients daily as part of routine post-operative follow-up with emphasis on identifying and addressing post-operative complications such as thromboembolic phenomena e.g. DVT. Patients with features of thromboembolic phenomena or develop other Serious Adverse

Events will be investigated thoroughly with blood work up PT-INR, aPTT and Doppler Studies for the lower limbs. They will receive treatment as per guidance of qualified physician.

Serious Adverse Events (SAE) shall be reported within 24hours of occurrence to Department Of Orthopaedics, SOMREC, and National Drug Authority (NDA) using National SAE reporting tools.

Patients shall be followed up for a period of 2 weeks post operatively.

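### The DSMB may stop for an undefined large efficacy effect in a single-arm trial where everyone receives tranexamic acid, which spares no one an inferior treatment and costs safety and transfusion data

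*Combined protocol and SAP*

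**What the plan says.** Section 3.1 sets the design: "This will be an open label single arm trial involving adult patients". The abstract confirms that treatment is the same for all: "Patients scheduled for open femoral shaft fracture intramedullary nail fixation surgery will receive preoperative tranexemic acid at 15mg/kg".

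Section 3.10.2 says that the DSMB "will meet when 50% data collection completed and 90% completed to perform an interim analysis", and section 3.10.1 gives the same two time points. Section 3.10.2 describes the planned interim analysis as one for efficacy, refers to a Bonferroni approximation, and sets alpha at 0.0001 for an omnibus test with 2 degrees of freedom.

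Section 3.10.3 gives two reasons for stopping. One is safety. The other is "When noted a large efficacy effect", with no numerical definition. The same section concedes that the null hypothesis may be tested more than once: "Because the DSMB could stop the trial for safety concerns as well as for a large efficacy benefit".

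Section 3.12 plans a one-sample t-test for the primary outcome and does not state the fixed value against which the mean is tested. Safety is analysed there as proportions of adverse events in the study group. Safety and transfusion are the two secondary objectives (section 1.6.2.2). On duration, section 3.4 says: "The study will be conducted over a period of 3 months from the date of ethical approval".

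**The concern.** The usual ethical ground for stopping early for benefit is that some participants are on a treatment now known to be worse. No such group exists here. Participants not yet recruited would receive tranexamic acid under the protocol in any case. The plan gives no other reason for an efficacy stop.

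The costs fall on the trial's own objectives. The precision of the adverse event and transfusion results depends directly on the number of patients. A stop triggered by a high interim result also selects a high estimate of blood-loss reduction, and the plan has no bias-adjusted estimate for that case.

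The boundary cannot be applied as written. A test with 2 degrees of freedom suits a comparison of three groups, or of two parameters. A one-sample comparison of a mean has one parameter. The DSMB would have to decide for itself what large means.

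**Working it through.** **Inputs.** Section 3.6.1: historical mean 3.31 g/dl, SD 1.56, expected reduction 30% (0.993 g/dl), 1.96 and 0.84 for 95% confidence and 80% power, 10% non-response. Section 3.10.2: looks at 50% and 90%, alpha 0.0001. Section 3.4: 3 months, taken as 13 weeks. Section 3.7.7: 2 weeks of follow-up.

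**The plan's own figure.** n = (1.96 + 0.84)² × 2 × 1.56² / 0.993² = 7.84 × 4.867 / 0.986 = 38.7, so 39. Then 39 / 0.9 = 43.3, which the plan rounds to 43. The figure reproduces. Half of 43 is 21 to 22, and 90% is about 39.

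**Mismatch of the boundary.** At alpha 0.0001 a chi-square test with 2 degrees of freedom has critical value 18.42. The one-sample t-test at the same two-sided alpha has critical value 4.84 at n = 21, 4.78 at n = 22 and 4.35 at n = 39. The plan does not link the two.

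**Reduction needed to cross**, using the t-test against 3.31 with observed SD 1.56, as critical t × 1.56 / √n:
- n = 21: 4.84 × 1.56 / √21 = 1.65 g/dl, or 50% of 3.31
- n = 22: 4.78 × 1.56 / √22 = 1.59 g/dl, or 48%
- n = 39: 4.35 × 1.56 / √39 = 1.09 g/dl, or 33%

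**Chance of stopping and estimate given a stop** (simulation, 400,000 trials, normal data, true mean 2.317 g/dl, i.e. a 30% reduction):

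| First look | Stop at first look | Mean estimate | Stop first at n = 39 | Mean estimate |
|---|---|---|---|---|
| n = 21 | 6.8% | 46% | 32% | 36% |
| n = 22 | 8.0% | 45% | 31% | 36% |

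Over all early stops the mean estimate is about 38%. Over all trials, stopped or not, it is 30.8% against a true 30%.

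**Sensitivity to what the plan leaves open.**
- Null of a 30% reduction (2.317 g/dl), a reading that section 3.12 allows: about 0.01% of trials stop early when the true reduction is 30%.
- DSMB judges largeness informally, represented by nominal 0.05 at each look with comparator 3.31: about 81% stop at n = 22, with a mean estimate of 33%.

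**Safety data lost.** If no event of a given type is seen, the one-sided 95% upper bound is 1 − 0.05^(1/n):
- n = 43: 6.7%
- n = 39: 7.4%
- n = 22: 12.7%
- n = 21: 13.3%

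For an event with an assumed true rate of 2%, the chance of seeing at least one case, 1 − 0.98^n, is 58% at n = 43 and 36% at n = 22.

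Patients may be dosed while the DSMB waits for data. Finishing on time needs 43/13 = 3.3 patients a week, or 43/11 = 3.9 if the last two weeks are kept for follow-up. Two weeks at that rate adds 7 to 8 patients, so 28 to 30 in all, and the bound is 10.1% to 9.5%.

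**Transfusion data lost.** At the same observed proportion, an approximate confidence interval is √(43/22) = 1.40 times as wide after a stop at 22.

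**Time gained.** A stop at 21 leaves out 22 patients, and 22/3.3 is about 6.7 weeks at most. A stop at 39 leaves out 4 patients, or 4/3.9 to 4/3.3 = 1.0 to 1.2 weeks.

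**The case against.** The strongest reply is that the rule will seldom matter. With alpha 0.0001 enforced, a midpoint stop is uncommon at the design effect. About four in five early stops fall at n = 39, where four patients are lost and the inflation is modest. This stands, and it limits the size of the point. It does not supply a reason to keep the rule.

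Three stronger readings are tempting, and the documents do not support them.

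- *The rule exaggerates the blood-loss effect.* This is true only given an early stop. Frequent stopping and large inflation also do not occur together: under informal judgement midpoint stops are common, but the estimate is about 33%.
- *The 90% review comes too late to act on harm.* A reader might infer this from the follow-up: "Patients shall be followed up for a period of 2 weeks post operatively". At 3.3 to 3.9 patients a week the last four are operated on in little more than a week. But the safety outcome in section 3.8.2 covers the perioperative period, which the operational definitions end at 72 hours. About 1.4 to 1.7 patients are operated on in 72 hours, so two or three of the last four may still be undosed, before any time the DSMB needs. Section 3.7.7 also requires daily review and reporting of serious adverse events within 24 hours, and section 3.13 warns of limited theatre capacity, which may slow accrual. Moving that review to before the midpoint would leave the second half of the patients without a DSMB review, so it is not a clear gain.
- *The rule can only do harm.* Section 3.2 says that tranexamic acid is not always used at this hospital, and section 1.3 intends the results to inform guidelines. Earlier reporting is therefore a conceivable benefit. It is small: some weeks at most, bought with an uncontrolled estimate from about half the patients.

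**Conclusion.** The point holds as a design weakness of moderate importance. An efficacy stop has no participant to protect in this trial. It takes data from two stated objectives, and its boundary does not match the planned test.

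The figures of 7-8% and 31-32% for early stopping, and of 45-46% and 36% for the estimates, rest on a comparator of 3.31 g/dl, SD 1.56, normal data, a true 30% reduction and two-sided alpha 0.0001 applied to the t-test. The choice of null matters most: with a null of a 30% reduction the rule is almost inert. The loss of safety precision at a midpoint stop does not depend on these assumptions. The zero-event bound rises from 6.7% to about 13%, or to about 10% if 7 to 8 more patients are dosed before the DSMB acts.

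Nothing here questions stopping for safety.

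**What to change.** - In section 3.10.3, delete "When noted a large efficacy effect" and revise the sentence on stopping for benefit and repeated chances to reject the null.
- In section 3.10.2, delete the interim efficacy test with its Bonferroni reference and its 0.0001 boundary.
- In sections 3.10.1 and 3.10.2, state that DSMB reviews are for safety and study conduct only.
- In section 3.12, state that the primary outcome is tested once, at the end, at the full two-sided 0.05 implied by the 1.96 in section 3.6.1.

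This changes wording only and needs no extra patients or meetings. The sponsor gives up the option to finish some weeks early. The timing of the safety reviews can be left to the sponsor and the DSMB.

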3.11 Data Management

The data collected by the tool will be checked daily and edited for completeness. The data will be entered into the computerized system particularly in Epi Data version 3.1. Following entry, range and consistency checks will be run for each variable to identify inadmissible values. In some cases in which it is impossible to correct errors in the data, a missing value code will be assigned.

3.12 Statistical analysis

Data will then be exported into a SPSS version 19 system which will be used for analysis. We will summarise the study population. We will use descriptive statistics such as means (standard deviations) or median and interquartile range (IQR) for continuous variables and proportions for categorized variables. We will also conduct appropriate statistical tests such as chi square or Fischer's test for categorical variables and a one sample independent T-test or wilcoxon sum rank test for continuous variables.

Objective 1: *To determine the effectiveness of pre-operative intravenous Tranexemic acid 15mg/kg on reduction of perioperative blood loss as estimated by difference in 72 hour postoperative and 2 hour preoperative Hemoglobin concentration in patients undergoing open intramedullary nailfixation offemoral shaftfractures in Mulago National Referral Hospital.*

We will assess for the hypothesis that TXA reduces perioperative blood loss by at least 30% using one sample independent T-test

Objective 2: *To determine effectiveness of pre-operative intravenous Tranexemic acid 15mg/kg on reduction of transfusion rates by 30% inpatients undergoing open intramedullary nail fixation offemoral shaftfractures in Mulago National Referral Hospital.*

We will conduct univariate analysis and adjust for effect modification and confounding.

Objective 3: *To determine the safety of pre-operative intravenous Tranexemic acid 15mg/kg in patients undergoing open intramedullary nailfixation offemoral shaftfractures in Mulago National Referral Hospital.*

We will assess for safety using descriptive statistics showing proportions of adverse events in the study group.

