3.6 Sample size estimation

3.6.1 Sampling Procedure

Comparison of Two Means (Minn M. Soe and Kevin M. Sullivan, Emory University)

$$n = \frac{(Z_1 + Z_2)^2}{(u_1 - u_2)^2} 2(S)^2$$

$$(u_1 - u_2)^2$$

n = Sample size in each group

Z₁ = 1.96 for 95% confidence level

Z₂ = 0.84 for 80% power

S = Standard Deviation of Outcome in Control Group

u₂ - u₁ = minimum meaningful difference between means

In study done in Mulago by Kajja et al estimated blood loss in 93 patient who underwent open femur shaft fracture intramedullary nailing estimated 72 hours postoperative mean total blood loss at 3.31g/dl, (SD 1.56).

Tranexemic Acid is expected to give 30% reduction in Blood Loss

i.e. $u_1 - u_2 = 0.3$

u₁

$$\underline{3.31 - u_2} = 0.3$$

3.31

$$u_1 - u_2 = 0.993$$

$$n = (1.96 + 0.84)^2 2 \times 1.56^2$$

$$0.993^2$$

$$= 38.7$$

[figure not shown]
$$n = 39$$

$$\text{Adjust for non-response} = 39 / 0.9$$

$$= 43.3 = 43$$

$$N = 43$$

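### Section 3.12 carries two-group methods into a single-arm trial: rank-sum cannot test blood loss against 3.31 g/dl, Objective 1 has no null value, and Objective 2 has no reference transfusion rate

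*Combined protocol and SAP*

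**What the plan says.** Section 3.1 fixes the design: "This will be an open label single arm trial". Section 3.12 gives a general list of methods. For categorical variables it offers "chi square or Fischer's test for categorical variables", and for continuous variables "a one sample independent T-test or wilcoxon sum rank test for continuous variables".

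The objectives follow. Objective 1: "We will assess for the hypothesis that TXA reduces perioperative blood loss by at least 30% using one sample independent T-test". Neither a null value nor a non-parametric alternative is given there. Objective 2 repeats the aim of a 30% reduction in transfusion, and its whole analysis is "We will conduct univariate analysis and adjust for effect modification and confounding".

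The only blood-loss benchmark is a historical local series of 93 patients, described in 3.6.1 as "estimated 72 hours postoperative mean total blood loss at 3.31g/dl, (SD 1.56"; section 1.4 also uses the 3.31. No reference transfusion rate is adopted anywhere. The 40% and 30% in section 2.3.3 are placebo-group rates from studies elsewhere.

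**The concern.** A rank-sum test needs two sets of individual observations. This trial will have one set, plus a published mean and SD, so the listed alternative to the t-test cannot address the primary question. The name given to the t-test joins a one-sample test to an independent-samples test, and the value to test against is left open. The phrase about a reduction of at least 30% could mean a null of 3.31 g/dl (any reduction, with 30% hoped for) or of 70% of 3.31 (a reduction shown to exceed 30%). These are very different claims.

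For transfusion the gap is wider. Univariate and adjusted analyses inside one arm can show which patients were transfused more often. They cannot show that transfusion fell, because nothing in them represents care without the drug.

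At stake is a choice made after the data are seen: which null value, which substitute test if blood loss looks skewed, and which outside transfusion rate. Each can move the conclusion towards benefit.

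**Working it through.** **Inputs.** Benchmark mean 3.31 g/dl and SD 1.56 (3.6.1); expected reduction 30%, so 0.3 × 3.31 = 0.993 g/dl (3.6.1); two-sided 5% (z = 1.96) and 80% power (z = 0.84) (3.6.1); n = 39 before and 43 after allowance for non-response (3.6.1).

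**1. The plan's own figure.** n = (1.96 + 0.84)² × 2 × 1.56² / 0.993² = 38.70, so 39. Then 39 / 0.9 = 43.3, given as 43 (strict rounding up gives 44). The figure reproduces, but the formula is for two groups and gives the size of each.

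**2. One-sample t-test against 3.31.** n = (1.96 + 0.84)² × 1.56² / 0.993² = 19.35, so 20, or 22 with the t distribution. For a true 30% reduction, power is 97.2% at n = 39 and 98.3% at n = 43. The test can be run and has ample power.

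**3. The same test against 70% of the benchmark.** The null is 0.7 × 3.31 = 2.317 g/dl. If the true reduction is exactly 30%, the null is true and the test favours the drug in only 2.5% of trials. At n = 39, a true reduction of 40% (difference 0.331) gives 25% power and one of 50% (difference 0.662) gives 73%. The unstated null value therefore decides whether the trial is well powered.

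**4. Rank-sum against one value.** Among 39 patients plus one constant, the constant can take 40 ranks. The smallest exact two-sided p is 2/40 = 0.05, however large the effect.

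**5. What a substitute would do.** The plan does not name the signed-rank test, but it is the usual one-sample replacement for rank-sum. It compares a median-type quantity with 3.31, which is a mean. If loss were lognormal with mean 3.31 and SD 1.56, the median would be 3.31 / √(1 + (1.56/3.31)²) = 2.99, which is 9.5% below the mean with no drug effect. Simulated trials (20,000 per shape, n = 39, no drug effect) gave these rates of falsely showing lower loss, against a nominal 2.5%:

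| Assumed shape | Signed-rank vs 3.31 | One-sample t vs 3.31 |
|---|---|---|
| Lognormal | about 11% | about 5% |
| Gamma | about 7% | about 4% |
| Normal | about 2.5% | about 2.5% |

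A percentile bootstrap interval for the mean gave 4.6% to 5.5% (lognormal) and 3.6% to 4.3% (gamma) in smaller runs, no real improvement on the t-test.

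**6. Transfusion.** A single proportion can be tested once a rate is fixed. As an illustration, take 8 of 39 transfused against an assumed 40%. The expected counts are 15.6 and 23.4, so chi-square = 7.6²/15.6 + 7.6²/23.4 = 6.17, p = 0.013; the exact binomial p is 0.014. With no rate in the plan, neither can be computed. Power of the exact binomial test at n = 39 (lower tail at most 0.025), over assumed reference rates:

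| Assumed reference rate | 30% relative reduction | 30-point absolute reduction |
|---|---|---|
| 30% | 14% | not applicable (rate would be 0) |
| 40% | 31% | 99.6% |
| 60% | 52% | 95% |
| 80% | 88% | 97% |

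Sections 1.4 and 3.12 do not say whether 30% is relative or absolute. Section 3.8.2 also defines the outcome as a number of units, whereas the objective speaks of transfusion rates.

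**The case against.** The strongest reply is that the list in 3.12 is generic. It is introduced by "We will also conduct appropriate statistical tests such as chi square" and assigns no test to any outcome. Objective 1 names only a t-test, one-sample fits the design, and the extra word can be read as a slip. Section 3.8.1 lists covariates such as anaesthesia type and nailing technique, for which chi-square, Fisher and rank-sum are proper within-arm comparisons.

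Most of this stands, and it rules out three stronger readings that a reader might infer:

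- That the primary analysis cannot be run. It can, as a one-sample t-test.
- That every listed categorical test needs two groups, so none could serve transfusion. Chi-square has a goodness-of-fit form for one proportion. The main obstacle is the missing reference rate, which would block an exact binomial test just as surely.
- That this trial faces an 11% false-positive rate. That figure belongs to a test the plan never names, under a skew that is assumed. The documents give only a mean and SD, and the outcome is a haemoglobin difference that can be negative, unlike a lognormal or gamma variable. With normal data there is no inflation.

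The reply does not rescue rank-sum as an alternative for blood loss, supply a null value for Objective 1, or give Objective 2 anything to be compared with.

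**Conclusion.** The point holds in a limited form. For Objective 1 the defect is one of specification: the test is usable once correctly named, but its null value is missing, and the only listed non-parametric alternative cannot be applied to the benchmark. The choice of null moves power at n = 39 from 97.2% (true reduction 30%, null 3.31) to 25% (true reduction 40%, null 2.317). These figures assume an SD of 1.56 and treat 3.31 as a fixed, known value.

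For Objective 2 the defect is substantive: a 30% reduction cannot be shown as the plan stands, because the analysis stays within the arm and there is no reference rate. The binomial powers rest on assumed rates. The signed-rank figures only illustrate why an unplanned substitute should be ruled out in advance. The matter is of moderate weight and should be corrected before analysis.

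**What to change.** Amend section 3.12 as follows.

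- **Objective 1.** Name a one-sample t-test of mean blood loss against a stated null: 3.31 g/dl if the claim is any reduction, or 2.317 g/dl if it is a reduction of at least 30%. Report the mean with its 95% CI. Do not use rank-sum for this objective.
- **Skewed data.** Keep inference on the mean. A bootstrap CI may be added as a sensitivity analysis only, since it does not cure the small-sample error. State that a signed-rank test against 3.31 will not be substituted.
- **Objective 2.** State and justify a reference transfusion rate, say whether 30% is relative or absolute, and report the proportion transfused with an exact binomial CI and a test against that rate. Reconcile this with the units-based definition in 3.8.2. If no rate can be justified, report the proportion descriptively and drop the reduction claim.
- **Other tests.** Label chi-square, Fisher and rank-sum as within-arm description.

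The cost is a few lines of text, with no extra patients or data collection. The price is that the transfusion conclusion may become less favourable: at n = 39, power for a 30% relative reduction is 14% to 52% for assumed reference rates of 30% to 60%.

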1.4 Research Hypothesis

Intravenous Tranexemic acid given preoperatively at 15mg/kg before open femoral shaft fracture intramedullary nailing will reduce average perioperative blood loss of 3.31 g/dl and perioperative transfusion rates by 30%.

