3.7.8 Total blood loss

Total blood loss due to the surgical procedure will be represented by total hemoglobin loss in the perioperative period.

Pre-operative hemoglobin (Pre-opHb) will be taken off 2 hours prior to surgery. Post-operative (Post-opHb) hemoglobin will be done 72 hours after surgery, it will be assumed hemodynamic stability is restored at that time.

Total Blood Loss = Pre-opHb – (Post-opHb + Blood Units g/dl)

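### The 80% power belongs to a two-group comparison, but the trial runs a one-sample t-test of at least 30% with no stated null; a reduction of about 15% could pass

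*Combined protocol and SAP*

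**What the plan says.** - **Design (3.1):** "This will be an open label single arm trial".
- **Sample size (3.6.1):** a two-means formula in which "n = Sample size in each group". The control value is an earlier series of 93 patients at the same hospital, with mean loss 3.31 g/dl and SD 1.56. The effect is stated as "Tranexemic Acid is expected to give 30% reduction in Blood Loss", that is 0.993 g/dl. With 1.96 and 0.84 for 95% confidence and 80% power, n = 39, raised to 43 for non-response.
- **Hypothesis (1.4):** TXA "will reduce average perioperative blood loss of 3.31 g/dl and perioperative transfusion rates by 30" per cent. It does not say which value is the null.
- **Primary analysis (3.12, Objective 1):** "We will assess for the hypothesis that TXA reduces perioperative blood loss by at least 30% using one sample independent T-test". No test value, sidedness, alpha or success rule follows.
- **Continuous variables in general (3.12):** "a one sample independent T-test or wilcoxon sum rank test for continuous variables", without saying which comparison each test serves.

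**The concern.** The sample size, the hypothesis and the test describe three different things. The size is for two concurrent groups. The hypothesis is a reduction of 30% or more. The test compares one mean with an unnamed constant.

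The choice of constant decides what a significant result means. Against 3.31, rejection shows that loss is below the historical mean by some amount and says nothing specific about 30%. Against 2.317 (70% of 3.31), rejection would support at least 30%, but the trial has almost no chance of achieving it at the effect it was planned for. Left open, the test can be run on the easy null and reported in the words of the hard one. Section 1.3 expects hospitals and the Ministry of Health to draw on the findings for guidelines, so the size of the claimed effect matters.

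In addition, 3.31 is itself an estimate, and a one-sample test gives it no sampling error. A rank-sum test cannot compare the arm with a historical mean at all, since it needs individual values in two groups.

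**Working it through.** **Inputs from 3.6.1:** historical mean 3.31, SD 1.56, 93 patients; difference 0.993; z-values 1.96 and 0.84; n = 39 and N = 43. **Assumptions:** the same SD in the new series, normal data, two-sided 5%, interim looks ignored.

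**1. The plan's figure.** n = (1.96 + 0.84)² × 2 × 1.56² / 0.993² = 7.84 × 4.867 / 0.986 = 38.70, so 39 per group, and 39/0.9 = 43.3. The arithmetic reproduces, but only for two groups of 39. Without the factor 2 the same formula gives 19.35; with the t distribution, 22 patients give 81% power.

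**2. One-sample test, null 3.31.**

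| | n = 39 | n = 43 |
|---|---|---|
| SE = 1.56/√n | 0.250 | 0.238 |
| Critical t | 2.024 | 2.018 |
| Power at a true 30% reduction (noncentral t) | 97.2% | 98.3% |
| Smallest significant reduction, g/dl | 0.506 | 0.480 |
| As % of 3.31 | 15.3% | 14.5% |

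An observed reduction of exactly 15.0% gives p = 0.054 at n = 39 and p = 0.043 at n = 43.

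**3. One-sample test, null 2.317.** At a true 30% reduction the null is exactly true, so rejection in the favourable direction has probability 2.5%. At a true 40% reduction it is 25% (n = 39). The observed reduction must reach (0.993 + 0.506)/3.31 = 45.3%.

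**4. Sampling error of 3.31.** SE = 1.56/√93 = 0.162, so the 95% CI is 3.31 ± 1.96 × 0.162 = 2.99 to 3.63. The SE of the difference is 1.56 × √(1/39 + 1/93) = 0.298, against the 0.250 that the one-sample test uses. Simulating the one-sample test with the historical mean drawn from its sampling distribution (2,000,000 runs) gives:
- two-sided error of 9.7% (n = 39) and 10.3% (n = 43);
- false benefit of 4.9% and 5.1%, against a nominal 2.5%;
- for a null of 0.7 × the historical mean, 7.3% and 7.6%, so the doubling applies only to the 3.31 null.

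**5. Comparison that carries the historical error.** For 39 against 93, power at 0.993 g/dl is 91.2% (43: 92.9%); simulated Welch tests give 90.8% and 92.7%. The smallest significant reduction at n = 39 is 0.589 g/dl, or 17.8%.

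**6. What at least 30% would need.** The SE of (new mean − 0.7 × historical mean) is 1.56 × √(1/39 + 0.49/93) = 0.274. The true reduction needed for 80% power is 0.30 + 2.8 × 0.274/3.31 = 53.2%; simulation gives 77.8% power at 53% and 81.2% at 54%. Fieller 95% intervals at n = 39:
- observed 15.3%: about −3% to 32%;
- observed 30%: 12.9% to 45.8%;
- the lower limit passes 30% between 46% observed (29.6%) and 47% observed (30.6%).

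**7. Sensitivity to the SD (null 3.31, n = 39).** For assumed SDs of 1.3 to 2.0, the threshold runs from 12.7% to 19.6% and power from 99.6% to 85.6%. Power falls to 80% only at an SD of about 2.16.

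**The case against.** The strongest reply is that the null is plainly 3.31. Sections 1.4 and 3.6.1 treat 30% as the expected effect, the objectives ask only about reduction, and the words at least occur only in 3.12. On that reading the sizing error is conservative, and a true 30% effect would be detected by either test. One sentence would then repair the plan. Most of this stands: the trial is not undersized on that reading, and no more patients are asked for. But naming 3.31 as the null does not make rejection evidence for at least 30%, which is the hypothesis 3.12 ties to the test.

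Other points, and what remains of them:

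- *Alpha is documented.* The 1.96 in 3.6.1 implies two-sided 5%, which agrees with the proposal. Section 3.12 should still say so. The interim level of 0.0001 in 3.10.2 barely changes it.
- *Against 3.31 as a fixed benchmark the error is 5%.* True. The figure of about 10% applies when the target is the mean of the untreated population that the 93 patients represent. A claim that TXA reduces loss needs that target.
- *A signed-rank test may have been meant.* Possibly; it would also treat 3.31 as exact.
- *Bias from a non-concurrent comparison is the larger threat.* This stands. Section 3.2 says intravenous TXA is already sometimes used at the site, and no test cures differences between the two series.

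**Conclusion.** The concern holds and should be fixed before data are seen. The stated 80% describes a trial that is not being run: the planned test has 97% to 98% power against 3.31, or 2.5% chance of success against 2.317 at the planned effect. Under the likelier 3.31 null, a reduction about half the hypothesised size is enough for significance, and the error rate is about twice nominal once the historical mean's uncertainty is counted.

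These figures rest on SD 1.56 in both series, normal data and two-sided 5%. The conclusion survives assumed SDs from 1.3 to 2.0. The 15% is approximate: just missed at n = 39, just met at n = 43.

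**What to change.** **In 3.12:**
- State H0 as no difference from the historical mean, two-sided 5%.
- Use a Welch t-test from summary values, t = (new mean − 3.31)/√(s²/n + 1.56²/93), and report the difference with its 95% CI.
- Report the percentage reduction with a Fieller or delta-method CI (or, equivalently, a CI for new mean − 0.7 × historical mean). Do not divide the interval by 3.31 as if it were exact.
- Claim at least 30% only if that whole CI lies beyond 30%, and say that this needs a true reduction of about 53% to 54% for 80% power. Otherwise claim only the reduction shown.
- Restrict the rank-sum test to contrasts within the arm, such as antegrade against retrograde nailing.

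**In 3.6:** replace the two-group text with 39 evaluable against 93 historical patients, about 91% power for 0.993 g/dl.

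**In 3.13:** add that this corrects sampling error only, not differences between the two series.

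**Outcome definition:** sections 3.7.8 and 3.8.2 define blood loss with and without a term for transfused units. Reconcile them first, and state that the outcome is defined as it was for the historical 3.31.

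**Cost:** wording only, no extra patients. The smallest significant reduction rises from about 15% to about 18% at n = 39, and the claim rule will probably not be met if the true reduction is 30%. Bias remains: if loss had fallen for other reasons by an assumed 0.1, 0.3 or 0.5 g/dl, the Welch test at n = 39 would still show false benefit in about 5%, 17% or 38% of trials (one-sample test: 9%, 25%, 50%).
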